5.2 Patients who lack capacity to consent for themselves

Where a patient is found to still lack capacity following administration of the loading dose, consent from a legal representative will be sought as soon as practically possible. Sites should aim to obtain consent within 72 hours of the patient being randomised into the trial.

In the first instance, the local research team will work to identify a **personal legal representative** as defined below:

A personal legal representative is a person independent of the trial, who by virtue of their relationship with the trial patient is suitable to act as their legal representative for the purposes of the trial and who is available and willing to act for those purposes.

The personal legal representative will be approached and will be provided with the Research Ethics Committee (REC) approved personal legal representative information sheet explaining the trial and the options for the patient's continuing involvement, including the need for them to give consent on behalf of the patient. The personal legal representative will then have time to consider the information provided, after which, a member of the local research team will ask when the personal legal representative would like them to come back and discuss participation further and potentially receive consent.

In the event that a personal legal representative cannot be identified, or it is deemed inappropriate to approach the potential personal legal representative, the local research team will work to identify a **professional legal representative** as defined below:

A person independent of the trial, who is the doctor primarily responsible for the medical treatment provided to that adult. Or a person nominated by the relevant healthcare provider.

Informed consent given by a professional legal representative shall represent the patient's presumed will. Where a professional legal representative gives consent, should a personal legal representative subsequently be identified they will be informed at the earliest opportunity and consent for the patient to continue in the trial will be sought from them.

If face-to-face consent is not possible, remote written consent may be undertaken. The informed consent discussions will proceed as above but by telephone, videoconference or equivalent. This written process will be undertaken in the presence of a witness who will initial the boxes on the ICF in response to discussions between the member of the research team and the legal representative. The member of the research team will then sign and date the ICF as will the witness. A copy of the completed ICF will be given to the patient and can be provided to the legal representative upon request. As above, a copy of the ICF will also be filed in the patient's medical notes, a copy will be sent to BCTU and the original placed in the ISF.

Should the legal representative decide that the patient would not want to take part, the patient will be withdrawn from the trial and no further data collected.

If the patient does regain capacity during the follow-up period, they will be asked to give consent for themselves using the process outlined in Section 5.1.

The patient's wishes (consent or refusal) will in all cases, supersede the legal representative's consent.

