10 WITHDRAWAL AND CHANGES IN LEVELS OF PARTICIPATION

Informed consent is defined as the process of learning the key facts about a clinical trial before deciding whether or not to participate. It is a continuous and dynamic process and patients should be asked about their ongoing willingness to continue participation at all visits. Patients should be aware from the beginning that they can freely withdraw (cease to participate) from the trial at any time. A patient may wish to cease to participate in a *particular* aspect of the trial.

Patients found to be ineligible post-randomisation (i.e. they were eligible at the point of randomisation but became ineligible over the course of the trial) should be followed up according to all trial processes and will still have their data analysed unless they explicitly change their level of participation.

The changes in levels of participation within the trial are categorised in the following ways:

No trial intervention: The patient would no longer like to receive the trial intervention but is willing to be followed up in accordance with the schedule of assessments (i.e., the patient has agreed that data can be collected and used in the trial analysis).

No trial related follow-up: The patient does not wish to attend trial visits in accordance with the schedule of assessments but is willing to be followed up at standard clinic visits (i.e., the patient has agreed that data can be collected at standard clinic visits and used in the trial analysis).

No further data collection: The patient is not willing to be followed up in any way for the purposes of the trial AND does not wish for any further data to be collected (i.e., only data collected prior to any changes of levels in participation can be used in the trial analysis).

The details of changes of levels in participation within trial (date, reason and category of status change) should be clearly documented in the source documents.

The Legal Representative and/or Researcher are also able to withdraw the patient for the above reasons.

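### Section 5.2 turns every legal-representative refusal into a full stop on data without reference to the graded levels in Section 10, so 90-day mortality may be lost where a lesser level would have been accepted

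*Protocol*

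**What the plan says.** Consent is deferred. Section 5 explains that nearly all eligible patients will lack capacity and that treatment cannot wait for a representative. Section 5.2 sets a 72-hour target for obtaining the representative's decision after randomisation.

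- **Section 5.2, refusal.** If the representative refuses, "the patient will be withdrawn from the trial and no further data collected". No lesser outcome is named at that point.
- **Section 5.2, information given.** The personal legal representative receives a sheet "explaining the trial and the options for the patient's continuing involvement, including the need for them to give consent on behalf of the patient".
- **Section 5.2, regained capacity.** A patient who recovers capacity during follow-up is asked for their own consent, and "The patient's wishes (consent or refusal) will in all cases, supersede the legal representative's consent".
- **Section 10, levels.** There are three: *no trial intervention*, *no trial related follow-up* and *no further data collection*. Under the first, "The patient would no longer like to receive the trial intervention but is willing to be followed up in accordance with the schedule of assessments". The second keeps data from standard clinic visits. The third keeps only data already collected.
- **Section 10, who may use them.** "The Legal Representative and/or Researcher are also able to withdraw the patient for the above reasons".
- **Section 16.6.** Patients without further data are censored at that point, and a sensitivity analysis for missing primary-outcome data is said not to be required.

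**The concern.** The representative's decision is the main point at which a randomised patient can leave the trial. By then the patient has been allocated and usually treated, so a refusal is in practice a change in participation, which is the subject of Section 10. Section 5.2 nevertheless names only the outcome that matches Section 10's third level.

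A representative may object only to the drug, or only to being contacted. Read literally, Section 5.2 discards the primary outcome in those cases too. The refusal comes after open-label allocation (Section 6.6) and after the early clinical course has been seen, so the loss need not be unrelated to prognosis or equal between arms. Deaths before consent stay in a minimal dataset (Section 5.3), while refusals arise only among patients still alive when the representative is asked. Section 16.3 expects at least 90 days of follow-up for everyone. An outcome that was never collected cannot be recovered by any later analysis.

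**Working it through.** **1. The passages side by side**

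| Situation | Section 5.2 | Section 10 |
|---|---|---|
| Representative objects to the drug only | Withdrawal, no further data | *No trial intervention*: scheduled follow-up continues, including day-90 mortality (Section 9.1) |
| Representative objects to trial contact only | Withdrawal, no further data | *No trial related follow-up*: standard clinic visit data kept |
| Representative objects to any data use | Withdrawal, no further data | *No further data collection*: earlier data only |
| Patient later regains capacity and consents | Patient is asked and their wishes override the representative's consent; effect on a prior refusal not stated | Not addressed |

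The sections agree only in the third row. In the second row, even Section 10 may not give the primary outcome, because a patient need not have a standard clinic visit at or near day 90.

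**2. The plan's sample size (Section 16.1)**

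Inputs: hazard ratio 0.73, two-sided alpha 0.05, power 90%, event rate 20%, 5% non-evaluable.

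- Events (Schoenfeld): 4 × (1.960 + 1.282)² / (ln 0.73)² = 425. The plan states 426.
- Risk in the better arm: 1 − 0.80^0.73 = 15.03%. Mean of 20% and 15.03% = 17.52%.
- Patients: 426 / 0.1752 = 2432. The plan states about 2430.
- Inflation: 2430 / 0.95 = 2558, rounded to 2560 as in the plan.

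The plan's figures reproduce.

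**3. What refusals would cost in power**

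The protocol gives no refusal rate, so f below is an assumption. As a worst case, refusers contribute no events.

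Events = 2560 × (1 − f) × 0.1752, multiplied by 0.95 if a full 5% is also lost for other reasons.
Power = Φ(√(events/4) × |ln 0.73| − 1.960).

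| Assumed refusal rate f | Patients | Events, no other loss | Power | Events, plus 5% other loss | Power |
|---|---|---|---|---|---|
| 0% | 0 | 448 | 91.5% | 426 | 90.1% |
| 1% | 26 | 444 | 91.2% | 422 | 89.8% |
| 5% | 128 | 426 | 90.1% | 405 | 88.6% |
| 10% | 256 | 404 | 88.5% | 383 | 86.9% |

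The power cost is modest across this range.

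**The case against.** **Different situations.** Section 5.2 deals with outright refusal, Section 10 with later changes, and the Section 5.2 outcome is one of the Section 10 levels. This stands in part: the passages overlap without being reconciled, and a reader who infers a flat contradiction goes too far. It does not remove the problem, because under deferred consent the refusal always follows randomisation.

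**Options are already mentioned.** Section 5.2 says the information sheet sets out options for continuing involvement. That sheet is not part of the protocol text, so it cannot be said that sites never offer lesser levels. The refusal sentence still gives sites a single instruction.

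**The patient's wishes prevail.** A reader might infer that Section 5.2 contradicts its own precedence rule. It does not: both stand in the same section, and no exception is made for patients whose representative refused. Section 9 also allows days 1 to 7 clinical data to be gathered retrospectively and day-60 and day-90 visits to be remote. What remains is a gap: the rule refers to the representative's consent and is silent on what follows a refusal.

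**Day-90 status is not always lost.** A reader might infer that nothing short of full participation keeps it. *No trial intervention* does keep it. The weakness is confined to the middle level.

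**Patients are not deleted.** Data up to refusal are usable and the patient is censored, so analysis by randomised group is not contradicted. This stands, but censoring does not recover vital status and assumes that leaving is unrelated to prognosis.

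**Ethics.** Whether data may continue after an outright refusal depends on consent rules outside the protocol. This stands and limits the fix to levels that the representative or patient actually agrees to.

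**Conclusion.** The concern holds as an unreconciled collection rule. Section 5.2 applied literally loses 90-day mortality in patients whose representative would have accepted a level that keeps it, and it leaves open what a patient's later consent restores.

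Its size cannot be fixed from the protocol. The 5% allowance covers refusals up to 5% with no other loss, at about 90% power. An assumed 10% leaves about 88.5%, or 86.9% on top of a full 5% other loss. A reader might treat the 5% allowance (0.05 × 2560 = 128 patients) as a shortfall, but that loss is already budgeted.

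A reader might also try to quantify bias by assuming unequal refusal between arms and high mortality among refusers. The protocol supplies neither figure, and refusers have by definition survived to the point of asking, so any such gap would come from the assumptions. Selective loss is plausible here but not shown. The change is worth making because the loss is avoidable, concerns the primary outcome, and is followed by censoring with no missing-data sensitivity analysis.

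**What to change.** Subject to REC approval:

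1. In Section 5.2, refer to the Section 10 levels. A representative who declines is asked which level applies, the choice is recorded on the Change of Status Form, and *no further data collection* is applied when that is the choice made.
2. In Section 10, reword *no trial related follow-up* so that, where agreed, it includes vital status and date of death to day 90 from routine health records, as well as standard clinic visits.
3. In Section 5.2, state that a patient who regains capacity and consents after a representative's refusal may have the interval data completed from records.
4. Align the information sheets, consent forms and Change of Status Form.

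The cost is a protocol and consent-document amendment and a slightly longer consent conversation. No extra visits are needed. A representative who wants all data collection to stop can still have that.

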5.3 Patients who do not survive

The most challenging ethical consideration in this trial relates to the inevitable death of some patients. Actively seeking out and informing relatives of trial participation is transparent and avoids potential distress were the family to discover at some future point that their relative had been involved in a clinical trial. However, informing the relatives/ friends of trial participation in the immediate aftermath of their relative/ friend's death will impose an additional emotional burden at a time of great distress. Previous and ongoing critical care trials have used passive information approaches, placing information in publicly accessible locations and in sites likely to be visited by relatives of the deceased (hospitals, GP surgeries, the offices of the Registrars of Births and Deaths). Such information contains brief details of the trial and contact details for those wishing to seek further information. This allows a relative to make an individual decision as to whether to seek further information regarding their relative/ friend, at a time of their choosing. This is the approach that we will take with the ABBRUPT trial and a REC approved poster will be placed in appropriate locations of participating sites.

Whilst every effort should be made to obtain consent as soon as possible following randomisation, there remains a risk that a patient may die prior to consent being obtained. In this instance, only a minimal, pseudoanonymised (trial number and age) dataset comprising of variables captured as part of standard of care will be transferred to BCTU. A Change of Status Form will also be completed for these patients.

5.4 Patients transferred to non-ABBRUPT sites during follow-up

There may be some situations where patients recruited to the ABBRUPT Trial have to be transferred to other hospitals. In these circumstances, with the patient's and/or legal representative's consent, the CI, ABBRUPT Trial Office and/or the research team at site shall engage with the non-ABBRUPT site to request a minimal dataset for the patient. The dataset requested will comprise both patient safety and compliance data.

6 ENROLMENT, RANDOMISATION AND BLINDING

6.1 Identification

Patients with NOAF will be identified by their existing clinical care team. As this may occur at any time of the day or night, sites should make efforts to ensure that a system exists whereby patients may be recruited and randomised at any time of the day and any day of the week. The local research team at site should be made aware of the randomisation at the first opportunity.

6.2 Screening and enrolment

Details of all patients approached about the trial will be recorded in REDCap ANNEX.

Prior to randomisation, a **medically qualified doctor or ACCP**, the name of whom will be captured on the Randomisation Form, **must** confirm eligibility.

6.3 Randomisation

Randomisation will be provided by BCTU using a secure online system thereby ensuring allocation concealment. Unique login usernames will be provided to those who wish to use the online system and who have been delegated the role of randomising patients into the trial as detailed on the ABBRUPT Trial Site Signature and Delegation Log. These unique login details must not be shared with other staff and in no circumstances should staff at sites access the system using another person's login details. Clinical team members who have been provided with the link to eligibility and randomisation training by the PI, will have a site-specific link provided to them on completion of the training to access the online randomisation system. The online system will be available 24 hours a day, 7 days a week, apart from short periods of scheduled maintenance. In the event of the online system not being available, a back-up telephone toll-free randomisation service ([name]) is available Monday to Friday, 09:00 to 17:00 UK time, except for bank holidays, government guided closures and University of Birmingham closed days.

6.4 Randomisation process

After eligibility for randomisation has been confirmed, the patient can be randomised into the trial using the online system. All questions and data items on the online Randomisation Form must be answered prior to a patient being randomised into the trial and a Trial Number being issued.

Following randomisation, a confirmatory e-mail will be sent to the PI and other delegates.

The site should add the patient to the ABBRUPT Patient Recruitment and Identification Log which links patients with their Trial Number. PIs must maintain this document securely and it must not be submitted to the ABBRUPT Trial Office. The ABBRUPT Patient Recruitment and Identification Log should be held in strict confidence.

6.5 Randomisation method

Patients will be randomised at the level of the individual in a 1:1 ratio to either Amiodarone or Beta-Blockade. A minimisation algorithm will be used within the randomisation system to ensure balance in the intervention allocations over the following variables:

- Hospital
- Age (≤ 60 years, >60 -<80, ≥ 80 years)

To avoid the possibility of the intervention allocation becoming predictable, a random element will be included in the algorithm. Full details of the randomisation specification will be stored in a confidential document at BCTU.

6.6 Blinding

This an open label trial with no blinding of the treatment allocation. Blinding is not possible as within the intervention arms, the choice of dose (and in the case of beta-blockade, the type) rests with the site.

6.7 Informing the patient's GP

With the patient's/their legal representative's permission, the patient's GP should be notified that they are participating in the ABBRUPT trial, using the ABBRUPT trial GP Letter.

7 TRIAL INTERVENTION

7.1 Trial interventions and dosing schedule

Patients will be randomised to either the intervention group (amiodarone) or the control group (beta-blockade). For the purposes of the trial, amiodarone and beta-blockers are defined as Investigational Medicinal Products (IMPs)

For those patients randomised to the intervention group, amiodarone will be prescribed according to the local treatment pathway and practice for AF. The treating clinician choosing the route of administration, dose and duration in accordance with local practice.

For those patients randomised to the control group, clinicians will prescribe the beta-blocker which aligns with their local treatment pathway and practice for AF. The beta-blocker choice should reflect local availability and familiarity. They may be administered enterally or intravenously; dosing should be according to local practice.

Patients will be treated with the allocated intervention until sinus rhythm has been maintained for 24 hours. Clinicians should then consider stopping the intervention according to local practice.

Compliance for ICU patients will be assessed from the observation and medication charts. The dosage of the intervention (amiodarone or beta-blocker) will be recorded up until Day-7 on the corresponding case report form (CRF).

7.2 Drug interaction or contraindications

As with all medications, there are common side effects with both beta-blockers and amiodarone. These are provided below:

Beta-blockers:

- Dizziness
- Headache
- Bradycardia
- Fatigue
- Gastrointestinal disorders

Amiodarone:

- Hypothyroidism
- Bradycardia
- Sleep disorders
- Eczema
- Decrease in blood pressure

Amiodarone has a long half-life; meaning there is potential for drug interactions to occur for several weeks (or even months) after treatment with it has been stopped.

7.3 Concomitant medication(s) / intervention(s)

Amiodarone can prolong the QT interval and therefore treatment with other drugs capable of prolonging the QT interval should be used with caution.

Antihypertensive agents should be used with caution in patients treated with beta blockade.

Clinicians should bear in mind that catecholamine-depleting agents or anti-sympathomimetic agents (e.g. clonidine, dexmedetomidine, reserpine) may have an additive effect when concomitantly administered with beta blockade with marked hypotension and bradycardia.

ABBRUPT: Protocol

Rescue medication for refractory AF that requires treatment is at the discretion of the treating physician. Any treatment given should be recorded on the drug log within the follow up CRFs.

The addition of calcium-channel blockers to beta blockers is permitted as long as the patient is on ICU and monitored for cardiodepression.

7.4 Prohibited medication(s) / intervention(s)

Both interventional treatments should be avoided in severe conduction disturbances (unless pacemaker fitted); in sinus node disease (unless pacemaker fitted); sino-atrial heart block (except in cardiac arrest); sinus bradycardia (except in cardiac arrest), atrio-ventricular blocks grade II or III, torsade de points.

Amiodarone should be avoided in iodine sensitivity and thyroid dysfunction.

Concomitant administration of beta blockade with verapamil or diltiazem is not recommended in patients with atrioventricular conduction abnormalities.

7.5 Intervention modification or discontinuation

Local Clinicians should monitor the patients and modify dosing or discontinue treatment should adverse effects become apparent. In particular, patients in both arms should be monitored for bronchospasm, bradycardia and higher degree heart block. Amiodarone may prolong the QT interval.

If an alternative treatment to the randomised intervention is commenced as part of standard of care, the participant will no longer be on the trial drug and will be followed up as Intention to Treat (ITT). This information will be captured on the subsequent CRFs.

7.6 Continuation of intervention after the trial

It is anticipated that patients will be treated until sinus rhythm has been maintained for 24 hours. Clinicians should then consider stopping the intervention according to local practice.

Patients who do not revert to sinus rhythm should be treated according to local practice. Patients who remain in AF at the end of their ICU stay should be managed according to local practice.

It is expected that both the intervention and control arm will be stopped upon discharge from the ICU unless there is a clinical indication for continuing them.

